5.2 Handling of Study Interventions

Study products, both active and placebo capsules, will be shipped directly from the manufacturer to the University of Florida's Investigational Drug Service (IDS) Pharmacy.

The products will be packaged in 200 ml amber glass or white HDPE bottles. The placebo (i.e. vegetable cellulose) will be similar to the active resveratrol product in terms of color, taste, size of capsule, and other aspects of appearance. The study coordinator or other members of the study team will not be able to distinguish the active product from the placebo. Thus, a double-blind design will be utilized.

Once acquired, the study product will be stored within the temperature-controlled drug room at the University of Florida's IDS. The product should be stored in cool, dry place according to instructions ($50 - 85^{\circ}F$ and $\leq 65^{\circ}RH$). The drug room of the IDS is locked and can only be accessed by designated personnel. Reference specimens are stored under specific conditions in regards to temperature and moisture controls.

At the time of randomization a signed order is received at the pharmacy, the pharmacist while following the study specific pharmacy plan will first verify the treatment arm to which the participant was randomized and re-package the appropriate amount of study agent/placebo capsules into Memory Cards (similar to blister packs). The pharmacist will dispense the appropriate number of Memory Cards for up to 40 daily doses to the study coordinator or designee. The study coordinator or designee will be responsible for dispensing the Memory Cards to the participant and instructing the participant to take daily doses (1 capsule following each meal – 3 times a day) until their next study visit, reminding the participant to return unused Memory Cards. Any unused study products will be destroyed by the company Steriocycle, on a bi-annual basis. Records of the study product destruction will be filed with the study's documents.

5.3 Concomitant Interventions

Concomitant Interventions are not allowed during this trial.

5.3.1 Allowed Interventions

No additional interventions are allowed during this trial.

5.3.2 Required Interventions

There are no required interventions to participate in this trial.

5.3.3 Prohibited Interventions

- Active treatment for cancer, stroke, peripheral vascular disease, coronary artery disease, myocardial infarction, congestive heart failure (stage III or IV), valvular heart disease, major psychiatric disease, severe anemia, liver or renal disease, diabetes, severe osteoarthritis, blindness or deafness, fracture in upper or lower extremity, upper or lower extremity amputation, or Parkinson's disease;
- Physical activity (i.e., running, bicycling, etc.) ≥ 120 min/week;
- Use of anabolic medications (e.g. growth hormones or testosterone), anticholinesterase inhibitor (e.g. Aricept), or anticoagulant therapies (aspirin use is permitted);
- Dietary supplementation of grape seed extract or ginko biloba;
- Consumption of any dietary supplements containing resveratrol, quercetin, or *P. cuspidatum*;
- Use of other Investigational products;
- Dietary supplementation with CoQ10 or alpha-lipoic acid.

5.4 Adherence Assessment

For this study, adherence will be defined as 90% or greater compliance with prescribed regimen, based on pill counts (number of pills consumed/number of days since previous visit). Study drug intake compliance will be assessed by means of capsule count by a study team member at 30, 60, and 90-day visits. In order to encourage high levels of adherence, a member of the study team will call each participant on a biweekly basis to encourage continued adherence.

The gold standard for clinical trials is by intent-to-treat. An analysis of the prognostic significance of actual dose consumed over the active period has value, but a comparison with placebo is not recommended. This would be a secondary analysis and would allow for determination of whether higher consumption while on active medication resulted in greater changes to outcome variables. For this study, a completers analysis will be performed on the target population of older adults (age ≥ 65 years).

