The proposed study will utilize a prospective, parallel design to determine whether 90 days of resveratrol supplementation in older men and women (\geq 65 years) is associated with (i) increases in muscle mitochondrial respiration, (ii) increases in levels of PGC-1 α , AMP-activated protein kinase (AMPK), and sirtuins (SIRT1 and SIRT3), and (iii) improvements in functional performance and metabolic parameters. To achieve these aims, 60 participants will be randomized to receive a placebo (n=20), 1000 mg/day of resveratrol (n=20), or 1500 mg/day of resveratrol (n=20) for a 90-day period. We will collect muscle specimens from the vastus lateralis at baseline and 90 days for biochemical analyses (see **Table 1** for planned data collection and procedures). In addition to the measures listed in **Table 1**, we will also monitor blood chemistries every 30 days at monthly clinic visits. To enhance retention and compliance, participants will receive biweekly phone calls throughout the 90-day treatment period. Following the completion of this trial, one in-person follow-up assessment will be conducted at approximately 30 days post-treatment to monitor blood chemistries and ascertain adverse events. In addition, approximately 10-days following muscle Biopsy procedure, a follow-up visit will take place to assure absence of biopsy complications and to monitor blood chemistries.

Eligible participants will be randomized to receive placebo (vegetable cellulose) or resveratrol product containing either 1000 mg resveratrol/day or 1500 mg resveratrol/day. In all conditions, participants will ingest three pills per day and will be instructed to consume one pill following each meal. Participant safety will be our highest priority, and we will monitor potential adverse events associated with resveratrol consumption by blood work analysis (complete metabolic panel and complete blood count), and assess reported adverse events using the National Cancer Institute (NCI) criteria during all study visits, including the 10 and 30-day follow-up visits.

Table 1.	Timeline fo	or tests, eva	luations, and	d protocols	to be conduc	cted and perf	ormed

Assessment	Phone Pre- Screen	Screenin g Visit	Baseline Visit 1	Baseline Visit 2	10 days Post- Biopsy Visit	30-Day Visit	60-Day Visit	90-Day Visit 1	90-Day Visit 2	10 days Post- Biopsy Visit	Follow- up 30 Day
Telephone interview pre- screening	X										
Informed Consent		X									

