Participants in all conditions will receive up to a 40-day supply of a resveratrol product or placebo, or a combination thereof for the 1000 mg/day condition. The reason participants will be provided with up to a 40 day supply is to ensure that they have a sufficient supply of study product before their day 30 visit, which will be scheduled at 30±7days from their second Baseline visit. Participants will also be given a up to 40 day supply at their day 30 and day 60 visits. Participants in all conditions will be instructed to consume three capsules per day, one capsule following each of their main meals (i.e. breakfast, lunch, and dinner).

Participants will also be asked to record taking their study product on a daily basis in a medication diary. Participants will also be asked to record any adverse events they may have experienced on this diary, as well as any concomitant interventions that they participated in since the previous study visit. If the participant reports any change in medications, including prohibited medications, during the study, this information will be recorded in the participant's file. Additionally, if the participant reports engagement in any prohibited interventions listed below, this information will also be recorded in the participant's file.

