Product Compliance: All medication containers, whether empty or containing unused tablets, must be collected to allow medication compliance to be determined (via a pill count) and to allow for proper destruction of the medication. Compliance will be measured by the number of pills returned at the visit compared to the number expected with 100% compliance. The research assistant will discuss the participant's adherence to medication since the previous clinic visit.

Adverse Event (AE) Assessment Toxicity (NCI) Criteria: At the designated intervals for event collection, participants will be asked the following question: "Since your previous visit, were you diagnosed with any new disease or condition, or experienced significant worsening of the diseases you were previously diagnosed with?" AEs will be obtained by self-report and will not require supporting documentation. AEs will be reported quarterly to the Independent Safety Board (oversight committee) and the NCCIH for each blinded treatment group.

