9.3 Definition of Populations

Intent-to-treat population for the primary outcome is synonymous to those getting baseline and three-month biopsies, whether or not they adhere to the treatment. Every effort will be made to bring back participants for their three month (post-treatment) biopsy visit, regardless of their levels of adherence. Intent-to-treat for serial measurements will include those with at least one of their follow-up visits. As above, we shall make every effort to get all follow-up visits completed, regardless of adherence.

The per protocol (PP) population will consist of all patients in the ITT population who are not major protocol violators. Specifically, PP population will consist of individuals who did not take any prohibited therapies during the trial, had $\geq 90\%$ adherence with prescribed regimen based on pill counts, and completed all baseline and post-treatment assessments.

The gold standard for clinical trials is by intent-to-treat. An analysis of the prognostic significance of actual dose consumed over the active period has value since it will allow for further analysis of dose effects. This will be a secondary analysis, and will allow for determination of whether higher consumption while on active medication results in greater changes to outcome variables. For this study, a completer analysis will be performed on the target population of older adults (age \geq 65 years).

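### The adherence formula in Section 5.4 leaves out the three capsules due per day: taken literally, 27 of 90 capsules (30%) reaches the 90% cut-off

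*Combined protocol and SAP*

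**What the plan says.** Section 5.4 states that "adherence will be defined as 90% or greater compliance with prescribed regimen", and adds in the same sentence how this is obtained: "based on pill counts (number of pills consumed/number of days since previous visit"). The counts are made three times: "Study drug intake compliance will be assessed by means of capsule count by a study team member at 30, 60, and 90-day visits".

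The regimen is the same in all three arms. Section 5.1 says "Participants in all conditions will be instructed to consume three capsules per day", and the opening synopsis says "In all conditions, participants will ingest three pills per day".

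Two other places bear on the definition. The Product Compliance paragraph of Section 6.2 says "Compliance will be measured by the number of pills returned at the visit compared to the number expected with 100% compliance". Section 9.3 makes at least 90% "adherence with prescribed regimen based on pill counts, and completed all baseline and post-treatment assessments" a condition for the per-protocol population, and gives no formula. By contrast, Section 9.3 defines the intent-to-treat set for the primary outcome as "those getting baseline and three-month biopsies, whether or not they adhere to the treatment".

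**The concern.** A percentage of the regimen needs the number of capsules due as its denominator. The bracket in Section 5.4 has days instead. With three capsules due each day, the result is three times too large as a proportion, and the 90% line falls at a little under one capsule a day.

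At stake is who counts as adherent in the reports and who enters the per-protocol set. A programmer who follows the bracket would admit participants who took less than a third of their product. A programmer who notices the fault would have to choose a repair, possibly after the capsule counts are known, and the plan would not say which repair to use.

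**Working it through.** **Inputs.** Cut-off 0.90 (Sections 5.4 and 9.3). Capsules due per day: 3 in every arm (Section 5.1). Nominal interval between counts: 30 days, with a window of 7 days either side (Sections 6.2.2 and 6.2.4), hence 23 to 37 days. Treatment period: 90 days. The plan gives no worked capsule count, so there is no figure of its own to reproduce.

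**Formulas.**
- Literal score = capsules taken / days. Fewest capsules that pass = 0.90 x days, rounded up.
- Score against capsules due = capsules taken / (3 x days). Fewest capsules that pass = 0.90 x 3 x days, rounded up.

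**At 30 days.** Capsules due: 3 x 30 = 90. Full intake scores 90/30 = 300% under the literal formula. The literal cut-off is 0.90 x 30 = 27 capsules, and 27/90 = 30% of those due. One capsule a day scores 30/30 = 100%, although only 30/90 = 33.3% of the regimen was taken. Against capsules due, the cut-off is 0.90 x 90 = 81.

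**Across the window and the whole period.**

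| Days | Capsules due | Literal score at full intake | Fewest capsules passing, literal | Fewest capsules passing, against capsules due |
|---|---|---|---|---|
| 23 | 69 | 300% | 21 (30.4%) | 63 (91.3%) |
| 30 | 90 | 300% | 27 (30.0%) | 81 (90.0%) |
| 37 | 111 | 300% | 34 (30.6%) | 100 (90.1%) |
| 90 | 270 | 300% | 81 (30.0%) | 243 (90.0%) |

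The fault has the same size at every interval, so it does not depend on visit timing or on whether the 90% is applied at each count or over the whole period.

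**Does Section 6.2 supply the missing formula?** It sets returned pills against an expected number that it does not state. Suppose a full 40-day supply is dispensed, the maximum under Section 5.1: 40 x 3 = 120 capsules. A fully compliant participant at day 30 has taken 90 and returns 120 - 90 = 30. The expected number could be the 90 to be taken or the 30 to be returned, and the text does not say which. The paragraph shows that full compliance with the regimen is the benchmark. It does not give a ratio that can be programmed.

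**The case against.** The best defence is that the bracket explains only how pills are counted, and that the result, in capsules per day, is then to be judged against the prescribed three. On that reading the cut-off is 0.90 x 3 = 2.7 capsules a day, or 81 of 90 over 30 days, which is correct. The sentence does refer to the prescribed regimen, so the reading is possible and very probably what was meant. But the comparison with three per day is a step the reader has to add. It is also fair that capsules due can be worked out from the fixed regimen, the dispensing log and the return counts in Section 5.1. This makes the repair cheap, but it does not make the bracket right.

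Four stronger conclusions that a reader might draw are not supported:

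- *That Section 9.3 sets a 30% threshold.* It does not repeat the bracket or refer to 5.4. It uses the same 90% pill-count criterion and leaves the formula open.
- *That the day-10 post-biopsy visit is the previous visit at the first count, so that the denominator is shorter still.* The schedule in Section 6.1 shows product neither dispensed nor counted at that visit. This reading would set about 30 days of capsules against about 20 days.
- *That temporary stops of treatment show the formula to be wrong.* How stop days should count is a separate missing detail. The documents give no stop lengths from which to judge its effect.
- *That the primary result is at risk.* The primary analysis set does not depend on adherence.

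**Conclusion.** The formula is wrong as written; severity is minor. It is a drafting error in the only adherence formula the plan gives: literally applied, it passes a participant at about 30% of capsules due instead of 90%.

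The effect is confined to per-protocol membership and adherence reporting. The primary analysis and power are unaffected. The secondary look at dose consumed uses the amount taken, not the 90% line. Section 9 assigns no specific analysis to the per-protocol set. A score of 300% would probably be noticed in programming, and the bi-weekly compliance review in Section 7.4 makes it less likely that low intake goes unseen, but neither corrects the text.

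The size rests on the stated three capsules a day and on the bracket being applied as it stands. The documents give no distribution of adherence, so the number of participants who would be reclassified is unknown.

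**What to change.** Replace the bracket in Section 5.4 with: (capsules dispensed minus capsules returned) / (capsules due since that supply was dispensed, i.e. 3 x days since the dispensing visit). Cite this one definition in the Product Compliance paragraph of Section 6.2 and in the per-protocol definition in Section 9.3, so that all three places use the same ratio.

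The cost is one sentence and two cross-references. Dispensing and return counts are already recorded under Section 5.1, so no new data are needed. The one drawback is that the per-protocol set may be smaller than under the literal formula, which is what a 90% criterion intends. The change does not touch the regimen.

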3. STUDY DESIGN

The proposed study will utilize a double-blind, placebo controlled, parallel design to determine whether 90 days of resveratrol supplementation in older men and women (\geq 65 years) is associated with (i) increases in muscle mitochondrial respiration (state 3 and 4), (ii) increases in levels of PGC-1 α , AMP-activated protein kinase (AMPK), and sirtuins (SIRT1 and SIRT3), and (iii) improvements in functional performance and metabolic parameters. To achieve these aims, 60 participants will be randomized to receive a placebo (n=20), 1000 mg/day of resveratrol (n=20), or 1500 mg/day of resveratrol (n=20) for a 90-day period. We will collect muscle specimens from the vastus lateralis at baseline and after 90 days of intervention, for biochemical analyses (See **Table 1** for planned data collection and procedures). In addition to the measures listed in **Table 1**, we will also monitor blood chemistries every 30 days at monthly clinic visits. To enhance retention, participants will receive biweekly phone calls throughout the 90-day treatment period. Following the completion of this trial, one in-person follow-up assessment will be conducted at approximately 30 days post-treatment, to monitor blood chemistries and ascertain adverse events. In addition, approximately 10-days following muscle Biopsy procedure, a follow-up visit will take place to assure absence of biopsy complications and to monitor blood chemistries.

Importantly, previous data demonstrate that 30 days of supplementation is sufficient for detecting meaningful changes in muscle mitochondrial biomarkers and clinical parameters in obese middle-aged adults, as proposed in the current study;[41] however, we propose to extend the supplementation duration to 90 days and to recruit a mixed population of men and women with diverse functional status. The justification for this extension is two-fold: our selected participant sample is comprised of older adults, who have been found to have lower levels of mitochondrial function than younger adults, and The RIPE Trial, our pilot resveratrol study, showed increased mitochondrial activity, as well as improvements in cognitive function, following a 90-day intervention.

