If all study entry criteria are met at the in-person screening visit, participants will be scheduled to return to the clinic for two baseline visits prior to randomization. During the first baseline visit, study staff will initially assess body mass and vital signs (e.g. pulse, blood pressure). Participants will then be asked to provide a fasting blood sample that will be utilized to evaluate clinical laboratory parameters. Following collection of the blood sample, participants will complete the following physical function tests: (1) the Short Physical Performance Battery (SPPB), (2) the Six Minute Walk Test, where participants will be asked to walk as far and fast as possible for 6-min on a 40 m track, and (3) isokinetic peak torque of the knee extensors and flexors of the dominant limb, unless contraindicated, will be assessed by dynamometer (Biodex Medical Systems, New York, NY) will be performed at this visit. Finally, the study coordinator will provide participants with a physical activity monitor. Participants will be asked to wear this monitor for a typical seven day period to objectively evaluate baseline physical activity habits. Also, during the Baseline Visit 1, study participants will be asked if they agree that left-overs of their tissue (muscle, blood) already collected for this study can be stored in the Tissue/Data Bank for future research. The Tissue/Data Bank has been approved by the UF IRB (IRB201300725, PI – [name], Department of Aging and Geriatric Research, University of Florida). The bank study has a separate consent form that needs to be signed by those who agree to participate in the bank.

Following this first baseline visit, participants will be invited to attend a second baseline visit to complete a muscle biopsy. Following completion of the Baseline Biopsy Visit, participants who satisfy all inclusion/exclusion criteria will be randomly assigned to receive resveratrol (1000 mg/day or 1500 mg/day) or placebo (vegetable cellulose). Participants will be provided with up to a 40-day supply of study drug capsules at the Baseline Biopsy Visit and will be asked to return to the clinic in approximately 30 days (± 7 days) for their 30-Day Visit.

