6.2.4 Follow-up Visits

30-Day Visit. Study compound compliance will be assessed by means of capsule count by a study team member. Additionally, the following procedures will be performed:

- Contact information will be updated, if necessary
- Vitals (blood pressure and heart rate)
- Blood draw for CMP and CBC w/differential
- Adverse events will be collected; NCI Toxicity Criteria will be used to determine severity
- Medical history update
- Product compliance

At the end of the visit, participants will be given a new supply of up to a 40-days supply of their randomly assigned study drugs, and will be asked to return to the clinic in approximately 30 days (± 7 days) for their 60-Day Visit. Participants will be asked to continue to follow the same dosing schedule as they did during Month 1. If this study visit is conducted late (outside of the allowable window), the target date for the 60-Day visit will be based on the date of the second baseline visit (BL2) which is when the participant started the study regimen.

60-Day Visit. Study compound compliance will be assessed by means of capsule count by a study team member. Additionally, the following procedures will be performed:

• Contact information will be updated, if necessary

- Vitals (blood pressure and heart rate)
- Blood draw for CMP and CBC w/differential
- Adverse events will be collected; NCI Toxicity Criteria will be used to determine severity
- Medical history update
- Product compliance

At the end of the 60- day visit, participants will be given a new supply of up to $\frac{a}{40}$ -days a 40-day supply of their randomly assigned study drugs and will be asked to return to the clinic in approximately one month (\pm 7 days) for their 90-Day Visit. Participants will be asked to continue to follow the study regimen schedule.

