Sensitivity analysis for Baseline Imbalance: Using baseline BMI, Baseline STATE 3, and gender, but not treatment, we shall develop a prediction equation via a linear model for the final STATE 3 value. Next, we shall use the predicted value for those missing the final STATE 3 value, and conduct permutation t-tests for each pair of treatments, replacing missing values by the predicted value. The type of bias that this corrects for is that missing values by be disproportionate in the arms according to the baseline value. For example, high baseline BMI may have more missingness on one arm while low BMI has more missingness on another. While this analysis corrects for interaction between treatment and missingness for baseline covariates, it does not account for missingness that develops during the study based on treatment vs. control issues. For example, if the treatment is associated with some subjects getting a headache and this leads to withdrawal from the study, this sensitivity analysis will not cover that contingency.

Sensitivity analysis for withdrawals for patient related study events, recognizing the events may not be measurable. First, we shall try to get a follow-up biopsy on every subject, ideally at the end of month 3, whether or not the subject completes the study medication program. Second, we shall ask the subject to provide reasons for withdrawal, based on a brief questionnaire. Third, we shall compare the withdrawal rates for the three treatment groups via an exact chi-square analysis. While an approximately equal withdrawal rate is not necessarily indicative of resolution, it is a reasonable assessment to make. Finally, using repeated measures mixed models methods, we shall compare the BMI trajectories for withdrawals vs. non withdrawals, stratified for treatment as a surrogate to the question as to whether the event of withdrawal is related to how the subject is doing on the trial. The month one and month two data will be used, as that will be missing for month 3.

Secondary analyses derived from the biopsy will be analyzed as above, but the study is powered strictly around STATE 3. Analysis on secondary variables that have repeated measures will utilize linear mixed model analysis of variance with unstructured covariance for repeated measures. Sensitivity analyses will be done via t-tests, utilizing the Satterthwaite correction for changes from baseline to three months, with last observation carried forward for missing data.

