9.4 Interim Analyses and Stopping Rules

No interim analyses are planned.

To determine the short and long term toxicities associated with administration of two doses of resveratrol when compared to a placebo in adults aged ≥ 65 years. The incidence, type, and severity of adverse events will be recorded during all phases of treatment and follow-up according to the Schedule of Activities shown in **Table 1**.

A single grade IV toxicity or two grade III toxicities will trigger an off cycle review by the DSMB, who can recommend suspension, amendment, or termination of the trial.

Toxicity due to this therapy is expected to be low. A description of each of the following study endpoints will be made at the conclusion of the subjects' accrual and 90 day post-treatment assessment:

- A. The number of subjects experiencing grades 1-5 adverse events according to Common Terminology Criteria for Adverse Events (CTCAE) v.3.0; the nature of these events; and the timing of their occurrence.
- B. The presence and magnitude of detectable change in blood chemistries.

Participants may have their treatment discontinued (permanently or temporarily) but remain on study for the following reasons; (a) unacceptable toxicity (≥ grade 3 toxicity) related to administration of resveratrol, using the toxicity criteria outlined in **Table 4**; (b) participant non-compliance with the study protocol; or (c) intercurrent disease, medication use, or condition that would affect the assessment of the participant's status. Of course, a participant is free to withdraw from the study at any time.

The study physician ([name]) will advise on whether or not he believes the participant should be removed or temporarily suspended from the study based on the toxicity criteria listed below.

Table 4. Dosage adjustment scheduled based on changes in blood chemistry values or participant report of clinically important symptoms.

Lab	Value	Placebo	Resveratrol 1000mg/day	Resveratrol 1500mg/day
WBC (n/μL)	< 3,000	Temporary Stop	Temporary Stop	Temporary Stop
Platelets (n/μL)	< 50,000	Temporary Stop	Temporary Stop	Temporary Stop
Creatinine Clearance (mL/min)	< 30	Temporary Stop	Temporary Stop	Temporary Stop
AST, ALT	> 2.0x ULN	Temporary Stop	Temporary Stop	Temporary Stop
Hematocrit	< 27%	Temporary Stop	Temporary Stop	Temporary Stop

Lab	Value	Placebo	Resveratrol 1000mg/day	Resveratrol 1500mg/day
Clinically Important Symptoms	Yes	Temporary Stop	Temporary Stop	Temporary Stop

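### The biweekly calls are not an adverse event contact, so in months 2 and 3 scheduled enquiry about adverse events can be about 37 days apart

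*Combined protocol and SAP*

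**What the plan says.** Three places describe the calls made during treatment. Section 5.4 says that "a member of the study team will call each participant on a biweekly basis to encourage continued adherence". The opening summary says: "To enhance retention and compliance, participants will receive biweekly phone calls throughout the 90-day treatment period". Section 3 says: "To enhance retention, participants will receive biweekly phone calls throughout the 90-day treatment period". None of them mentions symptoms or adverse events, and the calls do not appear in the Schedule of Evaluations (6.1).

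On adverse events, Section 6.2 says: "At the designated intervals for event collection, participants will be asked the following question". In 6.1 those points are clinic visits. After the baseline biopsy, participants "will be asked to return to the clinic in approximately 30 days (± 7 days) for their 30-Day Visit" (4.3). At that visit they "will be asked to return to the clinic in approximately 30 days (± 7 days) for their 60-Day Visit" (6.2.4). The 90-Day Visit follows about a month after the 60-Day Visit, again with a 7-day window.

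Other routes exist between visits. Participants note adverse events in a diary (5.1), are encouraged to ring the team (7.1), and have spontaneous reports recorded (7.3). The first month also has post-biopsy telephone calls at 24 hours and at 3 to 5 days (4.3), and a 10-day visit with adverse event assessment and blood work (6.1, 7.1).

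Table 4 in 9.4 is titled: "Dosage adjustment scheduled based on changes in blood chemistry values or participant report of clinically important symptoms". It lists symptoms as a trigger in all three arms.

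**The concern.** The team speaks to every participant between visits, but the stated purpose of the conversation is to keep the participant on product and in the study. Nobody is told to ask how the participant is. Section 7.1 names observation of symptoms as the main safeguard, and the symptom row of Table 4 depends on someone reporting a symptom. If a participant does not volunteer one, the call can pass with encouragement to continue, and the symptom may first reach staff at the next visit.

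What is at stake is the time from onset to review by the study physician. The gap is longest in months 2 and 3. For 1500 mg/day in older adults, the tolerability evidence in 7.1 comes from a four-week intervention, and the same section says that long-term side effects are unknown.

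**Working it through.** The plan states no figure for the interval between adverse event enquiries, so there is none to reproduce. The check is visit-window arithmetic.

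**Inputs**
- Baseline Visit 2 to 30-Day Visit: 30 ± 7 days (4.3, 6.2.2).
- 30-Day to 60-Day Visit: 30 ± 7 days (6.2.4).
- 60-Day to 90-Day Visit: one month ± 7 days (6.2.4).
- 10-day post-biopsy visit after Baseline Visit 2, with adverse event assessment (6.1). No window is given for it. The final 10-day visit has ± 3 days (6.2.5), and I assume the same window here for the upper figure.

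**Longest gap between scheduled enquiries = nominal interval + window**
- Month 1: 37 − 10 = 27 days. If the 10-day visit falls on day 7, 37 − 7 = 30 days.
- Month 2: 30 + 7 = 37 days.
- Month 3: one month is 30 or 31 days, so 37 to 38 days.

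Counting both windows from Baseline Visit 2 would allow day 23 to day 67, or 44 days. The text counts from the previous visit unless that visit was late, so I do not use 44.

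**With the question added to the existing calls**
- If *biweekly* means every two weeks: about 14 days between enquiries, and 90 / 14 = 6.4, so about 6 calls per participant.
- If it means twice a week: 7 / 2 = 3.5, so 3 to 4 days.

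**Average delay in months 2 and 3.** This is for an event that the participant does not volunteer, with onset spread evenly over the interval. The mean wait is half the interval: 30 / 2 = 15 days now, against 14 / 2 = 7 days with a two-weekly question.

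**Content of the question.** The scripted question in 6.2 asks about new diagnoses or marked worsening of conditions already diagnosed. A participant with a new headache, the plan's own example of a cause of withdrawal (9.2), could truthfully answer no. A call that only repeated the scripted question could miss it, so a second question about current symptoms is needed.

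**The case against.** The strongest reply is that silence is not exclusion. Nothing bars staff from asking about symptoms on a call. Section 7.3 requires adverse events to be recorded whether asked for, observed or volunteered, so a symptom mentioned on a call would be captured. With monthly active enquiry, a diary and an open invitation to ring, the plan already has a working adverse event system, and the first month has extra safety contacts. On this view what remains is a preference about a call script.

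Much of this stands. It confines the 37-day figure to months 2 and 3 and makes the point one of specification. It does not remove the gap. Call-in and spontaneous reporting depend on the participant, and no review of the diary between visits is described. Where the plan intends a call to serve safety, as with the post-biopsy calls in 4.3, it says so.

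A reader might go further and infer that participants who stop attending are never asked, that the reason for a missing second biopsy is lost, and that side effects are undercounted in one arm. The documents do not support this. Missed visits prompt immediate and repeated contact, including a second contact person and home visits (4.3), and home visits or calls are attempted for those who cannot attend (6.2.5). Section 8 continues follow-up, with permission, after product is stopped. Section 9.2 asks for reasons for withdrawal by questionnaire and seeks a follow-up biopsy on every subject. These steps do not name an adverse event question, but they rule out saying that nobody asks. The same section admits that its baseline-covariate imputation does not cover the case "if the treatment is associated with some subjects getting a headache and this leads to withdrawal from the study". That is a limit of the analysis and does not show that such events go unrecorded.

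**Conclusion.** The point holds as a low-cost improvement. The calls are specified for adherence, compliance and retention only. Scheduled staff-initiated enquiry can be about 37 days apart in months 2 and 3, and about 27 to 30 days apart in month 1. For participants who attend, the visit question looks back to the previous visit, so the effect is delay.

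Three stronger readings should be resisted.
- That the symptom rule in Table 4 is never reached: it acts on participant report, which 7.1 invites at any time.
- That 37 days at three capsules a day means 37 × 3 = 111 capsules taken after onset: this needs onset on the first day of the longest window, no call-in, nothing said on the intervening calls, and full dosing throughout.
- That the allowance of 20 − 18 = 2 non-completers per arm, or 6 overall, counts people whose symptoms go unseen: it is a power assumption in 9.2 and says nothing about why they leave.

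The 14-day figure rests on reading *biweekly* as every two weeks. The 30-day upper figure for month 1 rests on the assumed ± 3 days.

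**What to change.** In 5.4 and 6.2, make the existing biweekly call a recorded adverse event contact. It should open with the adverse event question and a question about current symptoms, both covering the time since the last contact so that events are not entered twice. Answers go on the adverse event form and to the study physician under the existing rules, and adherence is discussed only after that. List the calls as an adverse event collection point in 6.1, and define *biweekly*. No dose or clinical rule changes.

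The cost is protocol and form wording plus a minute or two per call, by the same staff. With about 6 calls for each of 60 participants, that is 60 × 6 = 360 calls, or 360 to 720 minutes (6 to 12 hours) over the whole trial. Slightly more minor events will be recorded. Every arm gets the same calls from staff blinded to assignment (6.2.3), so the extra recording should fall equally on all three.
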